2.3.2 Known Potential Benefits

Participants may receive direct benefit from being provided with the results of an exercise stress test and exercise prescription. Results are shared with each participant's cardiologist and entered under "research" in their medical record. Participants could also gain benefit from increasing their levels of PA. Finally, the information learned from the study could benefit future CHD survivors by possibly identifying a feasible, accessible, and acceptable intervention that can improve PA engagement in a population at risk for significant future cardiovascular morbidities.

3 OBJECTIVES

3.1 Study Objectives

A total of up to 90 young adults (ages 18 -25) are anticipated to be enrolled in Phase 1 of the study, which establishes eligibility for Phase 2. For Phase 2, the randomized trial portion of the study, we plan to enroll a total of 40 young adults. The aims of the study are to:

1. *Aim 1:* Evaluate the feasibility of the intervention.
Hypothesis 1: Young adults will rate participating in the intervention as enjoyable, easy, relevant, and useful.
2. *Aim 2:* Obtain qualitative feedback on session content and study procedures from participants using focus groups.

3.2 Study Outcome Measures

3.2.1 Primary Outcome Measure

Enjoyment of the intervention, ease of participation, applicability of session content, and helpfulness of the intervention.

3.2.2 Intervention Outcome Measures

Number of minutes spent in MVPA as measured by an accelerometer (primary intervention outcome).

Number of minutes spent being sedentary as measured by an accelerometer (secondary intervention outcome).

Maximal oxygen utilization during PA as measured by $VO_{2\max}$ during an exercise stress test (secondary intervention outcome).

3.2.3 Other Outcome Measures

Health-related quality of life as measured by the Patient-Reported Outcomes Measurement Information System (PROMIS).⁴⁶⁻⁴⁸

Self-reported PA as measured by the International Physical Activity Questionnaire (IPAQ).^{49,50}

3.2.4 Purported Mechanisms

PA attitudes as measured by the Benefits of PA questionnaire⁵¹.

PA subjective norms as measured by the PA Subjective Norms⁵² and the Social Support for PA⁵³ surveys.

PA perceived control as measured by the Barriers to Exercise survey⁵⁴ and the Self-Efficacy for Exercise Scale.⁵⁵

3.2.5 Other Exploratory Predictors

Cardiac-related anxiety as measured by the Cardiac Anxiety Questionnaire.⁵⁶

Self-consciousness of body due to cardiac interventions scars as measured by the modified Body Image Disturbance Questionnaire.⁵⁷

4 STUDY DESIGN

This single-site study is a randomized clinical trial of a Fitbit and exercise prescription vs. a Fitbit, exercise prescription, AND videoconferencing sessions with a PA coach over the course of 8 sessions in 20 weeks.

For Phase 1, participants are asked to complete less than 30-45 minutes of questionnaires wear an accelerometer for 7 days, and undergo an exercise stress test. Once the exercise stress test is completed and the accelerometer is returned, participants are compensated \$100. Parking and mileage reimbursement to/from the hospital is provided.

If a participant engages in <150 minutes of MVPA per week and has no contraindications on the exercise stress test, he/she is approached for participation in Phase 2. Once recruited, participants receive a Fitbit and an explanation of their exercise prescription based on the results of their exercise stress test as provided by an exercise physiologist. If the exercise physiologist is not available to develop the exercise prescription, the principal investigator, in consultation with the study physician, will develop the exercise prescription based on guidelines provided by the exercise physiologist. Next, study staff open an envelope (pre-prepared by the study statistician, [name]) to reveal the participant's study arm designation. Randomization is stratified by the number of minutes spent in MVPA per the accelerometer data in Phase 1 (≤ 25 min/day of MVPA vs. $\geq 26-59$ min/day of MVPA) with randomly varying block sizes.

Participants are randomized to 1 of 2 arms: the comparison arm, which receives a Fitbit and the exercise prescription, or the intervention arm, which also receives a Fitbit and exercise prescription PLUS videoconferencing sessions (e.g., FaceTime, Google Hangouts or Skype) with a PA coach (8 sessions over the course of 20 weeks). Each session lasts approximately 30 minutes and is audiotaped. The intervention arm focuses on changing attitudes (e.g., identifying pleasurable physical activities), perceptions of social norms of PA (e.g., problem-solving ways to receive support from family and friends) and perceptions of control for engaging in PA (e.g., increasing self-efficacy through goal setting and reducing barriers), as outlined by the Theory of Planned Behavior, to increase time spent in MVPA and decrease SB. The Fitbit is used to facilitate goal setting and self-monitoring for participants in the intervention arm.

During the course of the study, participants in both arms are asked to participate in an interim assessment (between weeks 8-12), which includes 30-45 minutes of questionnaires and wearing an accelerometer for 7 days, for which they are compensated \$50. Between weeks 20 and 26, participants in both arms are asked to engage in a post-intervention assessment, consisting of 30-

45 minutes of questionnaires, wearing an accelerometer for 7 days, and undergoing a final exercise stress test. Participants are compensated \$100. Parking and mileage to/from the hospital is compensated for their final exercise stress test. Upon completion of the post-intervention assessment, participants randomized to the intervention arm will be asked to participate in focus groups lasting approximately 1.5 hours, to discuss their study experiences. There will be 2 groups that meet via videoconferencing with 5-8 participants per group. Participants who attend the focus group will be compensated \$50.

Medical information also is collected from participants' online medical records to consider as covariates or moderators of the treatment effect, including sex and indicators of disease status (e.g., diagnosis, surgical history, functional class, number of medications, comorbidities, and the number of hospitalizations in the past year).

Physical activity coaches are graduate students pursuing advanced degrees in medicine, exercise physiology, or other health-related fields. They have undergone over 16 hours of training prior to working with the first participant and have completed all required human subjects training.

5 STUDY ENROLLMENT AND WITHDRAWAL

The total target sample size for enrollment in Phase 1 is up to 90 participants and in Phase 2, 40 participants (~17 participants per arm). A higher enrollment is expected for Phase 1 than Phase 2 to account for some participants being deemed ineligible to proceed with Phase 2.

Potential participants are identified through upcoming cardiology clinic rosters who meet the age (18 – 25 years of age) and diagnosis (moderate to complex CHD³) criteria. Study personnel check the patient's medical record to verify eligibility. If a patient appears to be eligible, study staff confirm with the attending cardiologist that no additional reason/s preclude the young adult from participating, including limitations to engaging in MVPA. Next, the patient is sent a letter from the attending cardiologist, notifying them about the study and that study personnel will be in contact. An “opt out” phone number is provided so that the potential participant can call and leave a message if they do not wish to be contacted. Approximately 1 week later, if no message was received, patients are called by study personnel. During the phone conversation, the objectives and primary components of the study are discussed. If a patient is interested, verbal consent is obtained for completing online questionnaires and the exercise stress test at NCH is scheduled. During the stress test visit, written consent for the stress test and accelerometer assessment is obtained. If a patient cannot be reached via phone, they are approached during their clinic appointment in person.

5.1 Participant Inclusion Criteria

Participants must meet all the inclusion criteria to be eligible to participate in the study. The criteria include:

- 1) Between 18 and 25 years of age
- 2) Diagnosed with moderate or complex structural CHD
- 3) Lives within 120 miles of NCH
- 4) Able to complete an exercise stress test on a treadmill

5.2 Participant Exclusion Criteria

Participants meeting any of the exclusion criteria at baseline will be excluded from the study. These criteria include:

- 1) Do not speak and write proficiently in English
- 2) Have a diagnosis of a genetic syndrome (e.g., Downs, Marfans, Wolf-Parkinson-White)
- 3) Have cognitive impairments that would interfere with completion of study measures
- 4) Have been engaged in a formal exercise program within the past 6 months, including cardiac rehabilitation
- 5) Have undergone open-heart surgery or have had a valve replacement in the last 3 months
- 6) Are prohibited to engage in MVPA by their cardiologist
- 7) Are unable to complete a treadmill-based exercise stress test
- 8) Are currently pregnant

After completing Phase 1, participants are approached for recruitment into Phase 2 unless they meet additional exclusion criteria, including:

- 9) Having contraindications for exercise based on an exercise stress test (e.g., exercise-induced arrhythmias or evidence of cardiac ischemia)
- 10) Exercising >150 min/week of MVPA per the accelerometer
- 11) Do not have internet access or a device for videoconferencing with a PA coach

5.3 Treatment Assignment Procedures

5.3.1 Randomization Procedures

The PI, study staff, and the research participant do not know the participant's arm designation until the envelope, which was prepared by the study statistician ([name]) is opened.

Randomization is stratified by the number of minutes spent in MVPA per the accelerometer data in Phase 1 (<25 min/day of MVPA vs. ≥26-59 min/day of MVPA) with randomly varying block sizes. Strata were based on the mean baseline levels of MVPA as reported in 2 studies of young and middle-aged adults with CHD.^{19,29}

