6.2 Phase 1: Enrollment/Baseline (T1)

Once the participant has consented, they are asked to complete an online questionnaire. The participant is also asked to undergo an exercise stress test and wear an accelerometer for 7 days. The stress test is completed at NCH within 3-4 weeks of recruitment and standardized feedback will be provided by an exercise physiologist, which includes their $VO_{2\max}$. Once completed, participants are compensated \$100 for their time for the baseline assessment.

Baseline online questionnaire:

- Socio-demographics characteristics
- Benefits of PA⁵¹
- Subjective Norms survey⁵²
- Social Support for Exercise survey^{53,55}
- Barriers to Exercise survey⁵⁴
- Self-Efficacy for Exercise Scale⁵⁵
- Patient-Reported Outcomes Measurement Information System⁴⁶⁻⁴⁸
- International Physical Activity Questionnaire^{49,50}
- Cardiac Anxiety Questionnaire⁵⁶
- Modified Body Image Disturbance Questionnaire⁵⁷
- Physical Activity Stages of Change Questionnaire – Algorithm⁵⁸
- Physical Activity Stages of Change Questionnaire - Continuous⁵⁹⁻⁶¹

VO_{2max}: VO₂ measurement is obtained via a graded exercise stress test on a treadmill. Exercise stress test results are used by the exercise physiologist to devise an exercise prescription that consists of recommendations for frequency, duration, intensity and type of PA. Exercise prescriptions are provided to participants if they qualify and enroll in Phase 2. Participants who are found to have an arrhythmia or show evidence of cardiac ischemia during exercise stress testing are immediately referred to their cardiologist for follow-up and are not eligible for Phase 2.

MVPA and SB: Participants receive a triaxial accelerometer (ActiGraph, model wGT3X-BT), sensitive to movement in all directional planes, to measure the amount of time spent in sedentary, light, moderate, and vigorous PA. The accelerometer is worn around the waist for 7 days for at least 10 hours per day, only to be removed when showering or submerging in water (e.g., swimming). Participants will also complete self-monitoring PA logs in the case they cannot wear the accelerometer (e.g. swimming). If baseline accelerometer and self-monitor PA log data indicate that a participant averages at least 150 minutes of MVPA per week, they are not eligible for Phase 2.

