Compensation: Participants are compensated \$100 for completing the baseline survey, exercise stress test, and wearing the accelerometer for at least 4 days (1 weekend day, 3 weekdays), for at least 10 hours per day. Additionally, participants' parking and mileage to/from the hospital for the exercise stress test are reimbursed.

Contact and Scheduling. If the participant is eligible for the Phase 2, they are contacted by phone and asked to schedule a home visit, within 8 weeks from their exercise stress test, if interested in participating.

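### The upper MVPA stratum for randomisation (26–59 min/day) lies above the Phase 2 entry limit of about 150 min/week (21.4 min/day), so on the ordinary reading the stratification does nothing

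*Combined protocol and SAP*

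**What the plan says.** **Strata.** Section 4 states: "Randomization is stratified by the number of minutes spent in MVPA per the accelerometer data in Phase 1". Section 5.3.1 gives the strata as "<25 min/day of MVPA vs. ≥26-59 min/day of MVPA) with randomly varying block sizes". Section 4 has the same upper stratum but words the lower one as at most 25 min/day. Section 5.3.1 says the strata come from mean MVPA in two studies of adults with CHD. Section 2.1 reports an average of 26 min from such a study.

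**Entry limit for Phase 2.** It is worded three ways:
- Section 4: "If a participant engages in <150 minutes of MVPA per week and has no contraindications on the exercise stress test"
- Section 5.2, as an exclusion: "Exercising >150 min/week of MVPA per the accelerometer"
- Section 6.2, as an exclusion: "participant averages at least 150 minutes of MVPA per week, they are not eligible for Phase 2"

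**Measurement.** Section 6.2: "The accelerometer is worn around the waist for 7 days for at least 10 hours per day". Section 5.2 uses the accelerometer alone, whereas Section 6.2 adds the log: "If baseline accelerometer and self-monitor PA log data indicate". A shorter wear period appears only as a condition of payment: "wearing the accelerometer for at least 4 days (1 weekend day, 3 weekdays), for at least 10 hours per day".

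**Purpose.** Section 2.1 says baseline MVPA will be used both to stratify and as an analysis covariate, and presents this as a gain in rigour over previous studies. Section 7.8 mentions no covariate and no comparison between arms.

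**The concern.** Eligibility and stratum both rest on Phase 1 MVPA, but one is stated per week and the other per day. Put on one scale, the cut between strata lies above the highest value an eligible participant can have. A likely cause is that the cut was placed near the mean of study samples that the protocol does not describe as restricted to inactive people, and was then applied to a group selected to lie below it.

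If so, everyone is in the lower stratum, and the stratification that Section 2.1 counts as a strength does no work. At stake is baseline balance on MVPA, which Section 3.2.2 names the primary intervention outcome. A report describing the trial as stratified by baseline MVPA would also mislead, and the same strata could be carried into the larger trial that this pilot is meant to inform.

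**Working it through.** The documents give no calculation for the strata, so there is no stated figure to reproduce. The check is a change of units, followed by a model for the size of the effect.

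**Step 1. One scale.** Inputs: limit 150 min/week (Sections 4, 5.2, 6.2); upper stratum 26–59 min/day (Sections 4, 5.3.1); 7-day wear (Section 6.2).
- Entry limit per day: 150/7 = 21.4 min/day.
- Lower-stratum bound per week: 25 × 7 = 175 min.
- Upper stratum per week: 26 × 7 = 182 to 59 × 7 = 413 min.

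The whole upper stratum exceeds 150. Whether exactly 150 is admitted makes no difference.

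**Step 2. Fewer wear days.** Suppose minutes were summed over k days without scaling and compared with 150:

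| k | highest eligible daily mean (150/k) | 26 × k | part of upper stratum reachable |
|---|---|---|---|
| 7 | 21.4 | 182 | none |
| 6 | 25.0 | 156 | none |
| 5 | 30.0 | 130 | 26 to under 30 |
| 4 | 37.5 | 104 | 26 to under 37.5 |

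The top of the stratum is out of reach even at 4 days (59 × 4 = 236).

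**Step 3. Accelerometer plus log.** Hypothetical case: 4 accelerometer days at 30 min and 3 non-wear days logged at 5 min. The combined total is 4 × 30 + 3 × 5 = 135 min, which is eligible under Section 6.2. The accelerometer-only mean is 30 min/day, which is the upper stratum. Under Section 5.2 (accelerometer alone, 30 × 7 = 210) the same person would be excluded.

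**Step 4. What an empty stratum costs.** With 20 per arm, the standard error of the difference in means is √(2/20) = 0.316 SD. The chance of a difference above 0.5 SD is 2(1 − Φ(0.5/0.316)) = 2(1 − Φ(1.58)) = 11.4%.

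Simulation for n = 40, 1:1, random blocks of 2 or 4, 10,000 replicates. These assumptions are not in the documents: weekly MVPA is lognormal, truncated at 150, with mean 26 × 7 = 182 before truncation (reading the 26 min in Section 2.1 as per day) and CV 0.4 to 1.0.

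| CV | 0.5 SD (min/week) | eligible median (min/day) | P(difference > 0.5 SD), strata as written | same, cut at eligible median |
|---|---|---|---|---|
| 0.4 | 11.2 | 17.2 | 11.3% | 0.8% |
| 0.6 | 14.5 | 15.0 | 11.3% | 0.6% |
| 0.8 | 16.6 | 13.1 | 10.9% | 0.5% |
| 1.0 | 17.9 | 11.5 | 11.8% | 0.3% |

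With the strata as written, a difference above 1 SD occurs in 0.1–0.2% of replicates.

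**Step 5. Sensitivity to the cut.** At mean 182, fixed cuts of 13 to 17.2 min/day give roughly 0.3–3.7%. If the distribution is set instead so that 21% exceed 150 min/week (Section 2.1's figure for U.S. adults meeting the guideline), the eligible median falls to 8.8–14.2 min/day and the chance rises to at most about 5%.

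**The case against.** The strongest reply is that little follows from this. The primary outcome is acceptability (Section 3.2.1), Section 7.8 plans no arm comparison, and Section 7.7 says the sample is neither powered for treatment effects nor meant for estimating effect size. That stands, and it caps the severity at minor. It does not remove the point: Sections 4 and 5.3.3 still refer to a treatment effect and to intent-to-treat analyses, so a comparison may be reported.

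Second, a reader might infer that the upper stratum must be empty on any reading. The documents do not support that. They state no rule for turning daily minutes into a weekly figure, and Steps 2 and 3 show two routes by which someone could reach it. Neither route is a stated rule, however. The 7-day wear and the weekly-average wording in Section 6.2 favour the times-7 reading, the 4-day minimum governs payment, and the log is meant for occasions such as swimming. The conclusion therefore holds with its condition attached.

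Third, the wording faults at the boundary carry little weight. The difference between below 25 and at most 25 could be a character lost in text conversion. The gap between 25 and 26 closes if whole minutes are used with the Section 4 wording. On the times-7 reading, nobody eligible is near 25 anyway.

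Fourth, advice on new strata may come too late. Section 14, effective March 2020, deals with home visits and with follow-up stress tests due at Week 22, which suggests that randomised participants were already in follow-up. That is a fair limit on the remedy.

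**Conclusion.** Wrong as written, and minor. All three wordings of the entry limit cap MVPA at about 21.4 min/day, while the upper stratum starts at 26. If weekly MVPA is the daily average times 7, or the sum over 7 worn days, the upper-stratum count is 0 of 40 and the stratification credited in Section 2.1 is inert. This needs no distributional assumption, only that conversion.

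The size is modest: about an 11% chance of a baseline MVPA difference above 0.5 SD (about 11–18 min/week), where a cut at the eligible median would give under 1%. The second figure rests on the assumed lognormal model; the first is close to the closed form.

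A reader might infer that the randomisation is compromised or that imbalance is unusually likely. Neither is supported. Allocation remains random, blocked and concealed (Sections 5.3.1, 6.3), and 11% is the ordinary value for any unstratified 20 versus 20 split. The feasibility and acceptability aims are unaffected. The cost falls on any reported arm comparison of MVPA, and on the accuracy of calling the trial stratified.

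**What to change.** **In any case.** Reconcile Sections 4, 5.2, 5.3.1 and 6.2 so that eligibility and stratum use one stated quantity (for example mean MVPA per valid day × 7), one data source and one worded limit. Where the limit should lie is for the sponsor to settle.

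**If randomisation is under way, as Section 14 suggests.** Keep the allocation list. Report the count in each stratum. If the upper one is empty, say that stratification had no effect and do not describe the arms as balanced by it. State in Section 7.8 that any reported arm comparison of MVPA is adjusted for continuous baseline MVPA, as Section 2.1 already says.

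**Only if nobody has been randomised and the entry limit stands.** Use two contiguous strata with a cut inside the eligible range, fixed before the first allocation. The exact cut is not critical: 13 to 17.2 min/day gives roughly a 0.3–5% chance of a difference above 0.5 SD under the assumed distributions.

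**Cost.** A short amendment, one added covariate and a sentence in the report, plus a new envelope list in the last case only. No extra participants or visits.

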5.3.2 Reasons for Withdrawal

Study participation is discontinued under the following circumstances:

- If participant's cardiologist determines that he/she is no longer eligible for the study due to a change in his/her cardiac condition.
- The participant requests withdrawal from the study.
- Development or reveal of any exclusion criteria (e.g., need for cardiac surgery).

5.3.3 Handling of Withdrawals

If withdraw occurs because a participant's cardiologist determines that the participant should no longer be in the study due to a change in medical status or the participant requests to be withdrawn, participants are asked to complete the assessments if possible and are included in intent-to-treat analyses.

5.3.4 Termination of Study

Because the AHA and American College of Cardiology indicate that receiving an exercise stress test is a standard of care and that CHD survivors with moderate to complex disease should be engaged in routine PA as long as it is deemed safe,⁷ termination of the study due to the development of adverse events is not anticipated. There are several procedures aimed to rule out any participants who may be at an increased risk of an adverse event due to the intervention. First, participants' cardiologists are asked about the eligibility of each potential participant. Second, participants undergo a baseline exercise stress test, in part, to rule out any cardiovascular contraindications for PA. If limitations in PA exist, these are incorporated into the exercise prescription developed by the exercise physiologist who conducted the stress test/principal investigator in consultation with the study physician, and the PA coaches work with participants on PA within the parameters of the exercise prescription. Participants' cardiologists have access to the results of the stress test, which are posted in participants' electronic medical record. However, the study will be terminated if the Data Safety Monitoring Board (DSMB) or IRB concludes, based on their findings, that termination is in the best interest of the participants.

